### 4.1.1. Treatment Population Characterization

The performance characteristics and available sizes of the VBX Stent Graft may lend itself to treating multiple pathologies in varying regions of the body. To facilitate better distribution of treated pathologies as well as to prevent a homogenous registry patient population, Gore has developed maximum enrollment goals for specific indications of device use in the registry. Treatment indications utilizing similar device use mechanisms will be grouped together into Treatment Categories. Use of Treatment Category classification will simplify study reporting and permit a common, pathology-based review of device experience.

Treatment Category Treatment Indication Example		Max Enrollment per Treatment Category*
	Peripheral artery aneurysm	
Lesion-exclusion (Non- iatrogenic in origin)	Pseudoaneurysm	
	Endoleaks	90
	Rupture	
Lesion-exclusion (latrogenic in origin)	Perforation	
(	Dissection	
	Snorkel / chimney technique with standard stent graft	
Visceral Perfusion	Fenestrated / branched stent graft component	140
	lliac-branched stent graft component	
	Arteriovenous fistula	
Luminal Pacanetruction	Arteriovenous graft	50
	Deep vein thrombosis	50
	Venous compression	
	Artery occlusive	
Occlusive Disease	Aortoiliac reconstruction with CERAB**technique	50
	lliac-in-stent restenosis	

\* The total enrollment from all reporting categories is not meant to equal 280 patients.
\*\* CERAB is defined as the use of three combined stents to create a new aortic bifurcation. A kissing stent technique will not utilize a

dedicated aortic component and is not within scope of the registry.

These treatment categories may also be used to report statistical analyses performed in an *ad hoc* fashion at the time of registry analysis and where the available patient population makes such analyses feasible.

## 4.2. Inclusion Criteria

For the purpose of registry enrollment and potential VBX Stent Graft implant, the following criteria should be evaluated at the time of Informed Consent Form (ICF) signature.

The patient is / has:

- 1. Age  $\geq$  18 years.
- 2. Signed informed consent form.
- 3. Endovascular indication for treatment based on treating physician's best medical judgment.
- 4. Intend for no other stents to be placed in the same peripheral vessel(s) targeted for VBX Stent Graft placement.
- 5. Willingness of the patient to adhere to standard of care follow-up requirements.

## 4.3. Exclusion Criteria

Due to its observational nature, exclusion criteria for registry participation is associated with the safe use of the device and the likelihood for an enrolled patient to contribute to registry analyses.

The patient is / has:

- 1. Known hypersensitivity to heparin or a previous incident of Heparin-Induced Thrombocytopenia (HIT) type II.
- 2. Participation in concurrent research study or registry which may confound registry results, unless approved by Gore.
- 3. Pregnant or breast-feeding female at time of informed consent signature.
- 4. Life expectancy < 12 months due to comorbidities.
- 5. Use of the VBX Stent Graft is for the treatment of *de novo* iliac occlusive disease.
- 6. Use of the VBX Stent Graft is for the treatment of aortic coarctations.
- 7. Use of the VBX Stent Graft in the coronary, pulmonary, carotid, vertebral, isolated infrarenal aortic, or vena cava vessels.

A rationale for each inclusion / exclusion criterion is located in **Appendix A**.

## 5. Registry Procedures / Reporting

The following sections provide information regarding registry expectations, in terms of its procedures, as well as the type of clinical data that may be captured as part of the clinical investigational plan.

Due to its observational nature, the registry will not require the use of any procedure and / or test and / or medical device different from those required by routine clinical practice for treating the investigated pathologies. Each site will be responsible for using and maintaining the equipment and medical devices in accordance with the manufacturer's directions and their institutional practices.

The sponsor will not impose requirements that limit health care professionals from exercising their best medical judgment for treatment. Therefore, patient selection, diagnostic imaging, and treatment interventions will be determined by physicians based on clinical practice standards.

5.1. Registry Procedures and Evaluation Schema

Figure 3. Registry Schema

### 5.2. Schedule of Events

A Schedule of Events is provided in **Table 2**. The described events are consistent with the anticipated standard of care for a person receiving a vascular stent graft. The timing and content of an individual patient's follow-up care regimen may differ from this expectation. Any device-related evaluations or the identification of an Adverse Event (AE) will need to be entered into the EDC system. Informed consent is required for all registry participants and is viewed as a protection measure in terms of patient's rights and welfare.

Table 2. Schedule of	Events
----------------------	---------------

#### 5.3. Informed Consent Process

All patients must provide informed consent prior to any registry-related data collection being performed. In an emergency procedure where it is not possible for the patient to provide consent prior to the implant, consent may be obtained afterward, but it should occur prior to discharge. The registry will be explained in a manner that avoids any coercion or undue improper influence on, or inducement of, the patient to participate. Patients will not waive or appear to waive their legal rights and any document will use native non-technical language that is understandable to the patient. The informed consent form (ICF) will include emergency contact details for any concerns. The case history (*i.e.*, source documents / patient chart) for each patient shall document that such informed consent was obtained. The Ethics Committee (EC)-approved consent form will be signed and personally dated by the patient and the person who conducted the informed consent discussion. The original signed ICF will be retained in the patient records. A copy of the ICF will be given to the patient for their records.

No patients deemed to be of a vulnerable population may be enrolled.

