### DEFINITIONS

Adverse Event: Any untoward medical occurrence, unintended disease or injury, or untoward clinical signs (including an abnormal laboratory finding) in patients, users, or other persons, whether or not related to the investigational medical device.

Adverse Device Effect: Adverse event related to the use of an investigational medical device.

**Clinical Investigation Plan:** A set of documents that describes the rationale, objectives, design and proposed analysis, methodology, monitoring, and the plan for the conduct of a clinical investigation. These documents may include the protocol, monitoring plans, and statistical analysis plans.

**Device Deficiency:** Inadequacy of a medical device with respect to its identity, quality, durability, reliability, safety, or performance. Device deficiencies include malfunctions, use errors, and inadequate labeling.

**Enrollment:** A patient is considered enrolled into the study once informed consent has been signed and dated.

Serious Adverse Event: An adverse event that led to death, serious deterioration in the health of the patient or led to fetal distress, fetal death, or a congenital abnormality or birth defect. Defined in more detail in Section 9.

Serious Adverse Device Effect: An adverse device effect that has resulted in any of the consequences characteristic of a serious adverse event.

**Unanticipated Serious Adverse Device Effects:** Serious adverse device effect which by its nature, incidence, severity, or outcome has not been identified in the current version of the protocol, Investigator Brochure (IB) or Instructions for Use (IFU).

PR	отос	OL SUMMARYi	ii
LIS	TOF	ABBREVIATIONS	v
DEF	INITI	ONS	vi
1.	Intro	duction	1
	1.1. 1.2.	Background Registry Rationale	1 1
2.	Regi	stry Objectives	2
	2.1.	Primary Objective(s)	2
3.	Regi	stry Design	3
	3.1. 3.2.	Description of Registry Design         Registry Endpoint(s)	3 3 3 4 5
4.	Stud	y Population	5
	4.1. 4.2. 4.3.	Description of Population 4.1.1. Treatment Population Characterization Inclusion Criteria Exclusion Criteria	5 6 7 7
5.	Regi	stry Procedures / Reporting	7

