### 3.2.2. Primary Endpoint

The primary endpoint of the VBX 17-04 registry is a composite of the following events reported within 30 days of treatment.

- Procedural Success
- Freedom from VBX Stent Graft-related Serious Adverse Event (SAE)

The first component, procedural success, describes the technical function of the VBX Stent Graft at the time of implant. The other component event, freedom from VBX Stent Graft-related SAE, is a description of short-term device safety. Possible endpoint events will be identified from site reports and adjudicated by a Clinical Events Committee (CEC) for reporting eligibility.

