#### 5.6. Procedure

The VBX Stent Graft implant procedure will be performed according to standard practice of the enrolling institution. As stated in the IFU, implanting investigators are advised to evaluate their patient for concomitant anticoagulation and / or antiplatelet medication therapy prior to and after the procedure. The necessity and choice of antiplatelet therapy can be individualize according to patient history as well as the pathology treated.

Any used VBX Stent Graft devices (implanted or opened but not implanted) will be recorded on the device accountability electronic Case Report Form (eCRF). It is recommended that a post-deployment angiogram is performed at the end of the procedure to assess device condition and efficacy of treatment provided that the patient's renal function is not prohibitive.

Procedural complications arising after enrollment of an eligible patient will be treated per investigator's best medical judgment as well as recorded in the EDC.

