## 9.1.3. Adverse Event Reporting and Coding

AEs will be reported on the appropriate eCRF and documented in the patient's permanent medical record. AE reporting will start from enrollment (when informed consent is obtained). The investigator at each site is ultimately responsible for reporting AEs to the sponsor.

The following information on each reported AE will be collected:

- Adverse event name
- Adverse event onset date
- Relationship
- Classification (serious or non-serious)
- Treatment
- Outcome
- Resolution date

AEs will be coded using the Medical Dictionary for Regulatory Activities (MedDRA).

- 9.1.4. Adverse event submission guidelines:
  - AE reporting begins once the patient is enrolled in the registry. All AEs should be reported from enrollment through registry completion / discontinuation.
  - Provide a diagnosis if possible. If unable to provide a diagnosis, report the symptoms as separate events. AEs should be reported using the full name without abbreviations or narratives.
  - AEs with an outcome status of "ongoing" should be assessed at each follow-up evaluation to determine if the event has resolved. AEs ongoing at study completion / discontinuation should be left as "ongoing" on the AE case report form.

The site principal investigator or designee must report SAEs to the registry sponsor as soon as possible after onset, observation, or first reporting of the occurrence, and in accordance with applicable national regulations. It is the responsibility of each investigator to report all SAEs to the reviewing EC, according to national regulations and EC requirements. A copy of the EC report will be forwarded to the sponsor. Source documents must be submitted upon request (*e.g.*, histopathology findings, catheter lab reports, etc.). All source documents must be blinded using only the patient's unique study identifier and forwarded to the sponsor.

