2.1.2 Secondary Endpoint(s)

Selected events that are illustrative of the device's potential impact to a patient from a safety perspective, overall device function described as patency or device durability captured as device integrity are to be as the registry's secondary endpoints. Possible endpoint events will be identified from site reports with some secondary endpoints within scope of CEC adjudication.

The secondary endpoints for the VBX 17-04 registry are the following:

- VBX Stent Graft-related death within 30 days post-treatment
- Procedural-related death within 30 days post-treatment
- Procedural-related SAE within 30 days post-treatment
- VBX Stent Graft patency (primary, primary assisted, secondary) through 30 days post-treatment
- VBX Stent Graft patency (primary, primary assisted, secondary) through five years post-treatment
- VBX Stent Graft-related SAE through five years post-treatment
- VBX Stent Graft-related death through five years post-treatment
- Loss of device integrity through five years post-treatment
- Limb salvage through five years post-treatment

Protocol Term	Definition			
Procedural Success	Technical Success (successful access, delivery, accurate deployment, and withdrawal of catheters) with patent VBX Stent Graft at end of procedure			
Patency	 Primary - Uninterrupted patency with no procedures performed on or at the margins of the treated segment. Primary Assisted - Any procedure performed in the treated segment before thrombosis that might prevent eventual failure. Secondary - Any procedure that restores patency after thrombosis. 			
Loss of Device Integrity	 Defined as any of the following: Device damage that compromises device functionality (stent fractures, graft tears, cuts, holes, delamination) Transient (compression) or permanent stent-graft collapse (invagination) following complete device deployment, resulting in an overall reduction in the vessel luminal diameter 			
Limb Salvage	Freedom from Major Tissue Loss—extending above transmetatarsal level; functional foot no longer salvageable ²⁸			
Reintervention	An additional unanticipated interventional or surgical procedure (including conversion to open surgery), related to the device (including withdrawal of the delivery system) or procedure. Anticipated or unanticipated status will be determined at the discretion of the investigator			

Table 1. Protocol Definitions

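### For emergency patients who consent after implant, the AE reporting start (consent) falls later than the start of the 30-day SAE endpoints (treatment), and no available text clearly requires SAEs in between to be entered

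*Protocol*

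**What the plan says.** Protocol 5.3 normally requires consent before any registry data are collected. It makes an exception for emergencies "where it is not possible for the patient to provide consent prior to the implant, consent may be obtained afterward", and adds that this should happen before discharge. It sets no limit in hours or days.

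The Protocol Definitions fix enrollment at the same moment: "A patient is considered enrolled into the study once informed consent has been signed and dated". Section 5.5 agrees. AE reporting is tied to that moment in Section 9.1.3, "AE reporting will start from enrollment (when informed consent is obtained"), and again in 9.1.4, "All AEs should be reported from enrollment through registry completion / discontinuation". Section 5.6 uses the same anchor for what is treated and recorded around the implant: "Procedural complications arising after enrollment of an eligible patient will be treated". Section 9 uses it for pre-existing conditions, which become AEs only if they worsen after enrollment.

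The endpoints use a different clock. The primary endpoint in Protocol 3.2.2 "is a composite of the following events reported within 30 days of treatment", and SAP 2.1.1 repeats this. A secondary endpoint in Protocol 3.2.3 and SAP 2.1.2 is "Procedural-related SAE within 30 days post-treatment". Protocol 3.2.2 also states where the events come from: "Possible endpoint events will be identified from site reports and adjudicated by a Clinical Events Committee (CEC) for reporting eligibility".

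**The concern.** For a patient who consents after implant, the two clocks start at different times. The interval in question contains the procedure itself and the period straight after it, when device- and procedure-related SAEs would naturally be looked for. A site that applies the 9.1.3 and 9.1.4 start point literally may enter none of them. Because endpoint events are identified from site reports, the Clinical Events Committee is not described as finding an event that was never entered, and the patient can then count as event-free.

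Two things are at stake. Any loss raises 30-day freedom from SAE and cannot lower it, and the confidence interval does not show it. Sites may also read the text differently, so the safety component may not measure the same thing everywhere.

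The group is foreseen by the plan. Protocol 10.3.3 expects both elective and emergent treatment, and the table in 4.1.1 lists rupture, perforation and dissection. Procedural success is judged at the end of the procedure and does not depend on the AE reporting period.

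**Working it through.** **Step 1: the two clocks for a late-consenting patient.**

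| Item | Start point | Where |
|---|---|---|
| 30-day SAE endpoints | Treatment | Protocol 3.2.2, 3.2.3; SAP 2.1.1, 2.1.2 |
| AE reporting | Enrollment, i.e. consent | Protocol 9.1.3, 9.1.4 |
| Procedural complications | After enrollment | Protocol 5.6 |
| Worsening of pre-existing conditions | After enrollment | Protocol 9 |

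The gap runs from implant to consent and is normally bounded by discharge.

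**Step 2: text that could close the gap.**
- Protocol 5.2 says identified AEs go into the EDC system; Protocol 9 says all AEs go on the eCRF. Neither gives an onset window.
- The SAE sentence in 9.1.4 obliges the investigator to report SAEs to the sponsor promptly after onset or observation, and does not itself mention enrollment. It sits under the same heading as the enrollment rule.
- Protocol 7.3 bars data entry before consent. It permits later entry of earlier events but does not require it.
- Protocol 9.2 and 9.3 send potential unanticipated device effects, suspected malfunctions with potential harm, and device deficiencies to the sponsor at once. These cover only part of the SAEs.
- Protocol 5.6.1 says entry after an unsuccessful procedure may include AEs.

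None clearly requires every SAE between implant and consent to be entered.

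**Step 3: the plan's precision figure.** SAP 2.0 states a margin of error below 6% with n = 280. The normal-approximation half-width at 50% is 1.96 × √(0.5 × 0.5 / 280) = 5.86%, which reproduces it. SAP 6.0 specifies exact binomial intervals. At the planning value of 93.6% (0.936 × 280 ≈ 262 patients), the exact 95% interval for 262/280 is 90.03% to 96.15%, so the half-width is (96.15 − 90.03)/2 = 3.06 points.

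**Step 4: size of the bias, under assumptions.** Let f be the share of patients consented after implant, and q the share of those with an endpoint SAE before consent that is not entered. The documents give neither. The overstatement is f × q. The largest q, 6.4%, is 100 − 93.6, from the SAP assumption on device- or procedure-related SAEs.

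| f (patients of 280) | q = 2% | q = 5% | q = 6.4% |
|---|---|---|---|
| 5% (14) | 0.10 points | 0.25 | 0.32 |
| 10% (28) | 0.20 | 0.50 | 0.64 |
| 20% (56) | 0.40 | 1.00 | 1.28 |

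In patients this is 280 × 0.0010 = 0.28 to 280 × 0.0128 = 3.58. To equal 3.06 points, q would have to be 3.06/f: 61%, 31% or 15% at f = 5%, 10% or 20%.

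**Step 5: a second parametrisation.** Take f × r × w, with r the 30-day SAE rate in late consenters and w the share of those events falling before consent and left out. With r = 6.4%, f = 5 to 30% and w = 25 to 75%, the result runs from 0.064 × 0.05 × 0.25 = 0.08 points to 0.064 × 0.30 × 0.75 = 1.44 points. If r is assumed to be 10 to 20% and f 10 to 30%, the range is 0.25 to 4.5 points. Of the 18 combinations tried there, only the most extreme (20%, 30%, 75%) exceeds 3.06.

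**The case against.** A reader might infer that SAEs before consent need not be reported at all. The documents do not support that. Section 9 says without a start point that all AEs are recorded on the eCRF, and the SAE sentence in 9.1.4 is mandatory and carries no enrollment anchor of its own. Section 9.1.3 can also be read as timing the act of reporting: nothing may be entered before consent, but the AE onset date is collected, so an earlier event could be entered once consent is signed. This stands, and it reduces the point from exclusion to conflicting text. It does not settle the matter, because the only sentences that define the reporting period point to consent.

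Look-back instructions could also sit in Tables 2 and 3, Figure 3 or SAP Sections 7 to 9, whose content is not available in the text reviewed, or in the separate CEC charter and registry guidelines. That is possible and cannot be checked here.

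On size, the 6.4% is a pooled device- and procedure-related rate, so it is a high reference for the device-related primary component, although emergency patients may differ from it. With no hypothesis test and no pass/fail rule, no formal decision changes. Both remarks are fair. They argue for a small amendment; they do not justify leaving two start points in a registry whose stated objective is safety and performance data.

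A reader might also infer that emergency patients unable to sign before discharge are shut out of the analysis. Protocol 5.3 says only that consent should precede discharge, and nothing bars later consent. What does follow from Protocol 10.3.2 is narrower: implanted patients who never consent, for example because they die first, are not in the analysis set.

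**Conclusion.** The point holds as an unresolved conflict over when SAE capture begins for patients who consent after implant. Capture can differ between sites, and any bias goes toward higher 30-day freedom from SAE.

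The size cannot be derived from the documents. On the main assumptions (5 to 20% late consent, 2 to 6.4% of those with an unentered endpoint SAE) it is about 0.1 to 1.3 points, or roughly 0.3 to 3.6 patients of 280. That is below the 3.06-point half-width, and only extreme assumed emergency rates exceed it. These values are the bias itself under the assumed inputs and should not be read as a limit on it. They apply to each 30-day SAE endpoint separately, since Protocol 9.1.1 allows one primary relationship per AE. The effect is probably small, but it is one-sided and cheap to remove, so it should be fixed.

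**What to change.** - In Protocol 9.1.3, 9.1.4 and 5.6, state that AEs are recorded from the earlier of consent or the start of the index procedure. For patients consented after implant, state that AEs since the start of the procedure are abstracted from the chart and entered once consent is signed.
- In Section 9, give the rule on worsening of pre-existing conditions the same start point.
- Add an eCRF field for consent before or after implant, and report the number consented late.
- Optionally, add a limitation sentence to the report: implanted emergency patients who never gave consent are not in the analysis set. Moving the AE start point does not recover them.

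Cost: a small amendment, with the ethics committee approval and site training that Protocol 6.4 requires; one eCRF field; a brief chart abstraction for late consenters only; and a check that the consent form covers use of those data. The reported SAE figure may be slightly less favourable. Treatment, endpoints and sample size do not change.

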#### 5.4. Pre-Procedure

In its management of the registry, Gore will not define the processes used to identify patients, conduct diagnostic imaging, or make medical decisions in the best interest of the patient. Physicians are encouraged to use their best medical judgment and to follow clinical practice standards in selecting patients for treatment with the VBX Stent Graft.

It is anticipated that most patients who will undergo an interventional procedure will have a physical exam with medical history, a review of their medications, and a laboratory evaluation of blood chemistries as part of standard procedure.

